All bioanalytical methods will be validated according to the FDA guidance on bioanalytical method validation. For each analytical batch, independent standard curves and quality control (QC) samples are included. The QC samples are included at the concentrations of lower limit of quantification (LLOQ), mid-range concentration and at a high concentration reflecting the highest concentration among the samples analyzed. A minimum of three QC samples at each concentration are included in each bioanalytical batch. These QC samples are independently prepared and controlled to assure day-to-day reproducibility and accuracy of quantification. For quality assurance, instrument performance is independently monitored using standard reference materials to confirm that sensitivity and system noise are within 20% of the day-to-day average.

The collected experimental data will be independently analyzed by two individuals of whom at least one is blinded to the treatments used during analysis. In case the two individuals reach discrepant results, a third scientist trained in the discipline will repeat the analysis and conduct an independent data verification to assess sources of discrepancy. No data points, experiments or individuals will be omitted from the analysis based on subjective assessment. Potential outliers will be evaluated by an independent expert in biostatistics who will determine whether an experimental observation is an outlier. In any situation where one of triplicate observations appears to be an outlier, an additional experiment will be conducted to allow determination of potential outliers.

Sex will not be assessed as a biological variable in this study as the focus of the proposal is pregnancy mediated changes in THC metabolism.

6. Regulatory

All AEs, regardless of whether they appear related to study participation, will be recorded and reported to the IRB annually.

AEs that are Grade 3 or higher (serious AEs) will be reported to the IRB and the Data Safety Monitor (DSM) within 24 hours of learning of the serious AE (SAE) and to NIDA within 5 working

days. Any actions taken by the IRB due to SAEs or AEs will be reported to NIDA within 24 hours of the notice of the IRB action.

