Dronabinol oral capsule is commonly administered to patients with loss of appetite. The recommended dose of dronabinol oral capsule is 2.5 mg twice daily. The dose may be reduced to 2.5 mg once daily for patients who are unable to tolerate higher doses. The dose may also be increased gradually based on response and tolerability. Treatment in this study is short-term (single dose). Short-term adverse events that can occur at a higher incidence than placebo include confusion, increased appetite, nausea and asthenia. Risks of these side effects are minimized by using the lowest clinically approved dose which adheres to the recommended dosage form: 2.5 mg once daily.

Estradiol patches are mainly used clinically in postmenopausal women with a typical replacement dose of 0.025-0.1 mg/24 hr. We expect transdermal estradiol at the administered dose (0.3 mg/24 hr) to increase circulating estradiol levels by ~200-280 pg/mL. Luteal phase estradiol levels can vary widely, from about 50-200 pg/mL. Thus, we anticipate that treatment will at least double estradiol exposure in most participants to ~250-480 pg/mL. This change in estradiol is the minimum needed to model the effects of estradiol on THC metabolism during pregnancy, when estradiol levels may reach 5,000-7,000 pg/mL. The risks of exogenous estrogens include increased risk of blood clots, elevations in blood pressure and plasma triglycerides, and increased risk of breast cancer and stroke in older women. Transdermal estradiol is the safest form of exogenous estradiol, and the risks of week-long dosing in pre-menopausal women are minimal. Nevertheless, as a conservative approach, we will exclude potential subjects with a history of blood clots, uncontrolled hypertension, moderate-severe hypertriglyceridemia, or a personal or family history of breast or ovarian cancer in a first degree relative. Short-term adverse events that can occur at a higher incidence than placebo include rashes, edema and elevated triglycerides. The subjects may also experience gastrointestinal changes and irritation, mood and sleep changes, headaches, hypertension, application site reaction, nausea, breast tenderness/swelling, changes in menstrual flow or cycle and leg cramps.

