- Occurrence of a medical condition within the exclusion criteria
- Pathologically changed laboratory values in subjects
- Participant becomes pregnant

A final study visit may be conducted for study volunteers who prematurely terminate the study, or for whom the study is discontinued by the DSM. This visit may entail a physical exam and/or laboratory tests as needed to ensure the participant's safety. If the study is discontinued prematurely for any participant because of an SAE, the adverse event will be documented with copies of all associated evaluations and laboratory studies; the investigator must exclude the subject from the study immediately and report the event to the Institutional Review Board and the DSM.

Process of AE/SAE collections, assessing by PI and DSM

The investigators will closely monitor the clinical protocols described in this submission to ensure the safety of volunteers. Subjects will undergo vital sign monitoring throughout the pharmacokinetic study visits as well as pregnancy tests at the screening visit and prior to each administration of dronabinol. Participants will be queried about AEs at all study visits and provided emergency contact information. An AE will be defined as any symptom or abnormal laboratory value that develops or increases in severity during the course of the study and is determined to be clinically relevant.

AEs are recorded at all study visits on dedicated forms and characterized in terms of their start and stop date, maximum intensity, action taken on trial medication, and subject outcome and graded as follows:

Grading of Adverse Events (AEs): AEs will be classified according to severity as below.

Grade 1: A Grade 1 complication is any reported side effect that does not require pharmacologic treatment. An example may be nausea, change in appetite, mild diarrhea or mild infection such as an upper respiratory infection or a headache.

Grade 2: A Grade 2 complication is any that requires pharmacologic treatment. These include minor conditions requiring treatment (e.g. a headache requiring medication).

Grade 3: A Grade 3 complication is one that requires surgical, endoscopic, or radiologic intervention. Grade 3a indicates that the intervention does not require general anesthesia, whereas intervention for a Grade 3b complication requires general anesthesia.

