Grade 4: A Grade 4 complication is any life-threatening complication that requires ICU level care. This may involve single organ dysfunction (e.g. dialysis, Grade 4a) or multi-organ dysfunction (Grade 4b).

Grade 5: Death of a patient.

Study investigators will monitor side effects and AEs at the study visits and the recording and reporting of all AEs will be as described above.

If a subject discontinues the trial because of an AE, this is also noted on the AE form. In the event of an SAE (grade 3 or higher), study investigators will complete and submit an Adverse Event Report form to our local IRB and the DSM (see below) within 24 hours of learning of the SAE. In addition, written summaries of the study status will be submitted to the local IRB and NIDA on a yearly basis, or more frequently if requested. Screening laboratory results are reviewed and signed by one of the study physicians on receipt from the clinical laboratory. Our clinical trial may be stopped if emerging effects demonstrate that the volunteers are at risk of SAEs from the study procedures.

8. Trial efficacy

Not Applicable. This study is not a Phase 3 efficacy trial and does not aim to assess efficacy or safety of a medication or device.

9. Administration of DSM Plan

The data and safety monitoring plan (DSMP) will be the responsibility of the study physicians Drs. [name] and [name] who will work closely with [name], PhD (Study PI), to ensure completeness of the DSMP. These individuals will closely monitor the clinical protocols described to ensure the safety of volunteers. When an individual subject completes the study, [name] will review the AE reporting and the study record for that subject. All adverse events, study enrollment and any relevant findings will be reported to the local IRB annually.

A detailed DSM report will be submitted to NIDA annually that includes a description of study progress, enrollment updates, retention and disposition of participants, AE and SAE listings and any regulatory issues such as amendments, protocol deviations, IRB reports and QA issues.

An independent DSM, [name], who is without conflicts of interest with regards to the study or the study investigators, will perform biannual reviews of this study.

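### Serious adverse events are defined only by a treatment-based grade, so a serious event managed without a procedure or intensive care gets no expedited report

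*Combined protocol and SAP*

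**What the plan says.** Section 6 (Regulatory) ties rapid reporting to grade: "AEs that are Grade 3 or higher (serious AEs) will be reported to the IRB". The IRB and the DSM are to be told within 24 hours, and NIDA is to hear of the same events within 5 working days. All other adverse events go to the IRB once a year. Section 7 (Trial Safety, under the process for AE/SAE collection) applies the same equation: "In the event of an SAE (grade 3 or higher), study investigators will complete and submit an Adverse Event Report form".

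The grades are in the same part of section 7, introduced by "AEs will be classified according to severity as below". The lower three are set by treatment:

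- Grade 1: "A Grade 1 complication is any reported side effect that does not require pharmacologic treatment"
- Grade 2: "A Grade 2 complication is any that requires pharmacologic treatment"
- Grade 3: "A Grade 3 complication is one that requires surgical, endoscopic, or radiologic intervention"

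Grade 4 needs an event that is both life-threatening and managed in intensive care. Grade 5 is death. No other criterion for seriousness appears in the document.

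The potential-risks text in section 7 says of one study drug: "The risks of exogenous estrogens include increased risk of blood clots, elevations in blood pressure and plasma triglycerides". It also mentions stroke, qualified as a risk in older women, and lists mood and personality changes among the possible short-term effects of hydrocortisone.

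**The concern.** A grade that records what was done to treat an event is being used to decide whether the event is serious. The two can part company. An event may put a participant in hospital, or leave lasting harm, and yet be managed with medication or observation only. Under the rule as written it falls below the reporting threshold.

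At stake is how soon people outside the study team learn of it. Under the stopping rules the DSM decides termination criteria for individuals and for the study from the data, so the timing of those data matters. The participants are healthy volunteers who, as section 7 states, gain no direct benefit.

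**Working it through.** No figure in the plan is at issue. The check grades hypothetical events by the section 7 definitions and follows each to its reporting clause.

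| Event and management | Grade | Expedited report? |
|---|---|---|
| Blood clot, drugs only, no procedure or intensive care | 2 | No |
| Stroke, drugs only, outside intensive care | 2 | No |
| Psychiatric reaction, admitted, drug-treated | 2 | No |
| Psychiatric reaction, admitted, no drug needed | 1 | No |
| Life-threatening event, drugs only, outside intensive care | 2 | No |
| Clot or stroke needing surgery or a radiologic procedure | 3 | Yes |
| Life-threatening event needing intensive care | 4 | Yes |
| Death | 5 | Yes |

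The first five rows are the gap. The last three show that the rule works where a procedure, intensive care or death is involved.

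For a Grade 1 or 2 event, the scheduled routes are these:

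- IRB: annual report (sections 6 and 9) instead of 24 hours, so a wait of up to 12 months.
- NIDA: annual report (section 9) instead of 5 working days, so up to 12 months.
- DSM: biannual review (section 9) instead of 24 hours. Read as twice a year, the wait is up to 12 / 2 = 6 months.

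Two other clauses were checked to see whether they restore prompt notice. The clause in section 7 on ending participation because of an SAE does require a report to the IRB and DSM, but it uses the same SAE term and so inherits the grade threshold. The review of each participant's record on completion (section 9) sets no deadline for outside notice.

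**The case against.** The best defence is that Grade 2 was meant for minor events. Its examples are minor conditions, such as a headache that needs medication. That may well be the intent, but the examples only illustrate; the definition covers every event needing drug treatment, sets no ceiling, and no rule lifts a serious drug-treated event to Grade 3.

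Several stronger readings are tempting, and the documents do not support them:

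- A reader might infer that such an event would be missed. It would not: adverse events are recorded at every study visit, each participant's record is reviewed on completion, and all events go to the IRB annually. Section 7 also allows IRB and NIDA summaries more often on request.
- A reader might infer that the participant could not be stopped. The SAE item in the stopping list would not apply, but the list also covers a condition that falls under an exclusion criterion, adverse events that cannot be tolerated, and investigator discretion. A clot or stroke falls under exclusion criterion b whatever its grade. None of these items sets a 24-hour report.
- A reader might infer that these are the main expected harms, or that they are usually managed with drugs. The plan ties stroke to older women, whereas participants are 21 to 45. It calls the risk of week-long transdermal estradiol in premenopausal women minimal and excludes women with a prior clot or stroke. It does not say how such events are usually treated. Nor does every drug-treated rise in blood pressure or change of mood count as serious.
- One event among 16 enrolled is 1/16 = 6.25%. That is the weight of a single hypothetical event, not its probability or the size of the flaw.

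The low expected risk and close physician supervision stand as reasons to think the rule would seldom be tested. They do not make it correct when it is.

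**Conclusion.** The rule is wrong as written: followed literally, it withholds expedited notice from serious events managed without a procedure or intensive care. The loss is one of time, with the delays calculated above. It does not affect detection, the ability to stop a participant, or the pharmacokinetic analysis.

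This rests on three assumptions: the grade definitions are applied as worded; biannual means twice a year; and no reporting route outside this document applies. The document gives no basis for estimating how often such an event would occur, so no frequency is claimed. The case for correction is that the rule concerns participant protection and is cheap to mend.

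**What to change.** Separate seriousness from grade:

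1. Define an SAE by outcome, whatever intervention was used: death, a life-threatening event, in-patient hospitalisation or its prolongation, persistent disability, or another medically important event.
2. Keep Grades 1 to 5 as a record of severity only.
3. In section 6 and in the AE/SAE process of section 7, replace the parentheses that equate an SAE with Grade 3 or higher by a reference to that definition.
4. Reconcile the other clauses that use the term. The SAE item in the stopping list and the clause on excluding a participant after an SAE would both change in reach. The sponsor should decide how they are to read under the new definition.

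The cost is a short protocol amendment, revised wording on the adverse event form and possibly a few more expedited reports. Under section 6, the amendment needs IRB approval and the NIDA program office's agreement before use. Dosing, sampling, sample size and the analysis are untouched.
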